5.4 Packaging and Labeling

Tilmanocept cartons ready for radiolabeling will be shipped and stored at the region-specific Cardinal Health radiopharmacy. Tilmanocept is provided in a vial. Vials are packaged as a kit. A carton contains five vials of tilmanocept. One kit, which is one tilmanocept vial, should be used for no more than one subject. The 400 µg dose groups will require two vials for each subject. The carton also contains five shield labels and 25 syringe labels. This package has been designed specifically for tilmanocept and protects the vials during shipment, handling, and storage. Navidea will provide a radiolabeling protocol and Quality Control worksheets.

Cardinal Health will radiolabel tilmanocept with the protocol group specified tilmanocept dose and the group assigned millicurie dose Tc 99m in 0.5 mL – 2.0 mL and deliver one syringe for the 50 and 200 µg doses and up to 2 syringes for the 400 µg dose to the clinical site radiopharmacy that is ready for administration.

5.5 Drug Logistics and Investigational Product Accountability

The investigator (or designated personnel) will confirm receipt of the investigational product in writing and will use the investigational product only within the framework of this clinical study and in accordance with this study protocol. For each subject, he/she will keep a record of the investigational product dispensed and store all other forms that accompanied the delivery of the radiolabeled product to the clinical site. These documents are to be filed in the investigator site file. Overall drug accountability and reconciliation will be completed by the sponsor or its representative. A list of investigational product vials and other materials that were returned, or destroyed, must be recorded and signed by the PI or an appropriately qualified designee as documented in the study site responsibility sheet. An overall accountability and reconciliation form of the investigational product will be prepared and completed. If there are any discrepancies, they must be investigated and their resolution documented. All unused study kits will be destroyed in accordance with institutional destruction procedures.

6 THERAPIES OTHER THAN INVESTIGATIONAL PRODUCT

6.1 Prior and Concomitant Therapy

All medications taken 30 days prior to Tc 99m tilmanocept injection through the post-injection safety follow-up will be documented. Subjects receiving radiation therapy or chemotherapy for a condition other than rheumatoid arthritis are not eligible for participation in the trial. The subject's history of treatments for rheumatoid arthritis will also be collected.

6.2 Post-Study Therapy

There are no post-study therapy restrictions.

7 STUDY PROCEDURES

7.1 Schedule of Evaluations

A schedule of evaluations is provided in the Schedule of Study Events (see [Appendix 1](#)).

7.2 Visit Description

7.2.1 Visit 1, Screening (Day -44 to Day 0)

All Subjects:

- Preliminary review of inclusion and exclusion criteria
- Obtain signed informed consent for study participation
- Allocation of unique subject number; this number will be used to document the subject data in the case report forms (CRFs) and enrollment log
- Demography – date of birth, gender, race
- Medical/surgical history- all relevant prior medical and surgical conditions will be recorded in the CRF. Documented medical conditions will also note the month and year of onset if the condition is still active.
- Concomitant Medications (within 30 days before injection).
- Vital signs (body temperature, heart rate, blood pressure, and respiratory rate after at least 1 minute in a resting position)
- ECG – The Electrocardiogram (ECG) reading will be assessed for clinical significance by the investigator, and any clinically significant abnormal findings will be noted on the subject’s medical history.
- Clinical laboratory tests – study subjects will have blood obtained for hematology, chemistry, and RA panel (see [Section 8.6.2.4](#)).
- Urine collection for routine urinalysis
- A urine pregnancy test for women of child-bearing potential. Females of child bearing potential are defined as women that are not surgically sterile (hysterectomy or bilateral oophorectomy) nor postmenopausal for at least 1 year prior to screening. Women who are not of childbearing potential will not require a pregnancy test.
- Physical examinations will include an assessment of height, weight and calculation of BMI and an examination of general appearance, skin, eyes, ears, nose, throat, head and neck (including thyroid), lungs, heart, abdomen, lymph nodes, musculoskeletal, and nervous system. Any clinically relevant finding is to be documented as a baseline finding. Physical exams that are conducted as standard of care prior to signing informed consent may be used if they are performed within 30 days of injection.
- RA Evaluation: The swollen and tender joints will be identified and documented during by physical examination as established by the 2010 ACR/EULAR, a DAS28 evaluation and a characterization of the subject’s RA history including previous treatments, date of symptom onset and date of diagnosis.
- Final confirmatory review of inclusion and exclusion criteria

Changes in health occurring after consent and prior to the day of injection will be added to the subject's medical history unless related to a study procedure.

7.2.2 Visit 2, Baseline (Day 1)

All subjects will be assessed for adverse events in an ongoing manner from the day of injection through the end of participation.

7.2.2.1 Before Administration of Tc 99m Tilmanocept

The following procedures will be completed for all subjects on the day of injection prior to the administration of Tc 99m tilmanocept:

- A urine pregnancy test for women of child-bearing potential. Females of child bearing potential are defined as women that are not surgically sterile (hysterectomy or bilateral oophorectomy) nor postmenopausal for at least 1 year prior to screening. Women who are not of childbearing potential will not require a pregnancy test.
- Assessment of adverse events
- Concomitant medication review
- ECG within 15 minutes prior to administration of Tc 99m tilmanocept
- Vital signs after at least 1 minute in a resting position (body temperature, heart rate, blood pressure, and respiratory rate) within 15 minutes prior to administration of Tc 99m tilmanocept

A PK blood sample will be collected for Subjects in Groups 10 and 11 within 15 minutes prior to the administration of Tc 99m tilmanocept.

7.2.2.2 Administration of Tc 99m Tilmanocept

IV administration of Tc 99m tilmanocept will be at study time 00:00. The preferred site of IV placement will be the left or right antecubital vein unless both elbows are primary sites for RA imaging, then the site for IV placement will be between the elbow and the wrist.

The filled syringe(s) will be connected to the Y-port for a slow push injection. At the completion of the injection(s), a 10 cc sterile normal saline flush will be administered.

The IV administration will be performed in the nuclear medicine department by an onsite Certified Nuclear Medicine Technologist or Nuclear Medicine Physician. Subjects will be continuously monitored for adverse events during the Day 1 Baseline Visit.

7.2.2.3 After Administration of Tc 99m Tilmanocept

Groups 1-9

For subjects enrolled in Groups 1-9, the following procedures will be completed at the specified times:

- Within 15 Minutes (00:01 to 00:15) Post Injection:
 - Assessment of adverse events
 - ECG (completed before vital signs)
 - Vital signs after at least 1 minute in a resting position (body temperature, heart rate, blood pressure, and respiratory rate)

- 60 ± 15 Minutes Post Injection:
 - Assessment of adverse events
 - Whole body planar imaging (anterior/posterior views)
 - Planar image with both hands in the FOV (5 min anterior/posterior views)
 - Additional 3D SPECT or SPECT/CT will be obtained on identified joints of interest.

- 180 ± 15 Minutes Post Injection:
 - Assessment of adverse events
 - Whole body planar imaging (anterior/posterior views)
 - Planar image with both hands in the FOV (5 min anterior/posterior views)
 - Additional 3D SPECT or SPECT/CT will be obtained on identified joints of interest.

Groups 10-11

For subjects enrolled in Groups 10-11, the following procedures will be completed at the specified times:

- Immediately following administration of Tc 99m Tilmanocept (00:00), a PK blood sample will be drawn.
- Within 15 Minutes (00:01 to 00:15) Post Injection:
 - ECG (completed before vital signs)
 - Vital signs after at least 1 minute in a resting position (body temperature, heart rate, blood pressure, and respiratory rate)
 - Assessment of adverse events
- 15 ± 5 Minutes Post Injection:
 - Assessment of adverse events
 - PK blood sampling
 - Whole body planar imaging (anterior/posterior views)

- **60 ± 15 Minutes Post Injection:**
 - Assessment of adverse events
 - PK blood sampling
 - Whole body planar imaging (anterior/posterior views)
 - Planar image with both hands in the FOV (5 min anterior/posterior views)

- **180 ±15 Minutes Post Injection:**
 - Assessment of adverse events
 - PK blood sampling
 - Whole body planar imaging (anterior/posterior views)
 - Planar image with both hands in the FOV (5 min anterior/posterior views)

7.2.3 Visit 3 Follow Up and End of Study

18-20 Hours Post-Injection (Groups 10-11):

The following procedures will be conducted 18-20 hours after administration of Tc 99m tilmanocept at the final end of study visit for subjects enrolled in Groups 10-11:

- PK blood sampling
- Whole body planar imaging (anterior/posterior views)
- Vital signs
- ECG
- Physical Exam, including body weight
- Clinical Labs
- Urinalysis
- Concomitant medication review
- Assessment and review of adverse events

5± 2 Days Post-injection (Groups 1-9):

The following procedures will be conducted 3 to 7 days after administration of Tc 99m tilmanocept and the final end of study visit for Subjects in Groups 1-9:

- Vital signs
- ECG
- Physical Exam, including body weight
- Clinical Labs
- Urinalysis
- Concomitant medication review
- Assessment and review of adverse events

8 PROCEDURES AND VARIABLES

8.1 Population Characteristics

8.1.1 Demographic and Other Baseline Characteristics

Up to 48 evaluable subjects may be enrolled. Up to thirty-six (36) female or male subjects ≥ 18 years of age with evidence of active RA will be enrolled in Groups 1-9. Three (3) female and three (3) male subjects aged ≥ 18 without evidence of active RA (HC) will be enrolled in Group 10. Three (3) female and three (3) male subjects aged ≥ 18 with evidence of active RA will be enrolled in Group 11.

8.1.2 Medical and Surgical History

Relevant medical and surgical histories will be obtained on all study subjects.

As part of the medical history, the date of the last spontaneous menstruation will be recorded, if childbearing potential is not excluded by surgical sterilization.

8.1.3 DAS28 Evaluation

All subjects will be evaluated a single time at screening (Visit 1) for the Disease Activity Score (DAS) 28 ([Prevoo et al, 1995](#)) assessment.

The DAS28 will be calculated from four components: tender joint count (TJC), swollen joint count (SJC), Visual analogue scale (VAS) of the subject's global health, and the laboratory parameter erythrocyte sedimentation rate (ESR). The formula used to calculate the DAS28 score is: $DAS28 = 0.56*\sqrt{(TJC)} + 0.28*\sqrt{(SJC)} + 0.70*LN(ESR) + 0.014*VAS$. See [Appendix 5](#) for details.

A DAS28 score of higher than 5.1 is indicative of high disease activity, whereas a DAS28 below 3.2 indicates low disease activity. A subject is considered to be in remission if they have a DAS28 lower than 2.6

8.1.4 2010 ACR/EULAR Classification Criteria

All subjects will be evaluated at screening using the 2010 ACR/EULAR Classification Criteria as part of eligibility and inclusion.

The 2010 American College of Rheumatology (ACR)/European League Against Rheumatism (EULAR) classification criteria includes four components: number and site of involved joints, serologic abnormality, elevated acute-phase response and symptom duration. See [Appendix 4](#) for details.

A total score of 6 or higher (out of a possible ten) combined with clinical synovitis not better explained by another disease confirms a diagnosis of "definite RA" ([Aletaha et al](#)).

8.1.5 Prior and Concomitant Medication

All prior medications used within the last 30 days before the first screening examination through the follow-up safety visit will be documented. An assessment of RA treatments will also be collected.

8.2 Tc 99m Tilmanocept Preparation and Administration

Based on the dose group the subject is enrolled in, the dose of Tc 99m tilmanocept should be ordered from Cardinal Health once the subject has been scheduled for IV administration and imaging.

In Nuclear Medicine, prior to initial imaging, an indwelling catheter will be placed for venous access. The preferred site of IV placement will be the left or right antecubital vein unless both elbows are primary sites for RA imaging, and then the site for IV placement will be between the elbow and the wrist.

The filled syringe(s) will be connected to the Y-port for a slow push injection. Immediately after the completion of the injection, a 10 cc sterile normal saline flush will be administered. Injection of Tc 99m tilmanocept will be at study time 0:00.

8.3 SPECT/SPECT-CT Image Acquisition

The camera used to obtain the images should be a dual-headed SPECT or SPECT/CT camera equipped with a low-energy, high-resolution collimator with a 15% window (20% can be used if 15% setting not available) centered over a 140keV peak.

The camera must have passed the daily SPECT QC tests as per the manufacturer's recommendation for that day's scan schedule.

Whenever possible subjects should be asked to void after injection and prior to the first imaging session and again between imaging sessions.

Subjects should be positioned supine with arms at their side. The subject's head, legs, hands, and hips should be in the true anterior position. The subject should be instructed to remain as motionless as possible during the scan, and asked to breathe as shallowly as comfortable when the camera is passing over the chest. To help minimize leg motion, a light taping around the ankles can be used to keep the legs together. A pillow under the knees is often very helpful for comfort.

A whole body (head to toe) planar scan using auto-contour should be obtained at the following time points:

Groups 1-9 (see [Appendix 2](#)):

- 60 ± 15 minutes post administration
- 180 ± 15 minutes post administration

Groups 10-11 (see [Appendix 3](#)):

- 15 ± 5 minutes post administration
- 60 ± 15 minutes post administration
- 180 ± 15 minutes post administration
- 18-20 hours post administration

It is anticipated that the whole body scan would be acquired for 25-30 minutes. Using state-of-the-art 2-headed cameras (nominal 20" x 15" FOV) a target of 5-7 million counts should be obtained for the summed view of both heads. For the higher activity injections, it may be possible to attain this target in a shorter time, allowing the subject more time off the bed between scans.

A simple measure of the subject's "thickness" (i.e. from a lateral visual view, the height of the subject's anterior-most chest/abdomen above the scan bed) should be documented. This will be used for the attenuation correction to be applied to the anterior/posterior views obtained from the whole body scan.

Following the whole body acquisition, a planar image with both hands in the FOV should be acquired for ~ 5-7 minutes in both the anterior and posterior view for subjects in Groups 1-9 and subjects in Groups 10 and 11 at 60 ± 15 and 180 ± 15 minutes post-administration .

For subjects enrolled in Groups 1-9: Following completion of the the planar imaging session at 60 minutes, a 3D SPECT or SPECT/CT should be obtained on Joints A and B, followed by a patient break. Following the 180 minute whole body scan, and planar image of the hands, 3D SPECT or SPECT/CT will be repeated for joint A and completed for joint B and/or C in accordance with the prioritization below. No greater than 3 SPECT or SPECT/CT imaging sessions will be obtained after the whole body planar imaging session.

In the event that multiple joints of interest are identified during whole body planar imaging, and the planar image of the hands, the following prioritization will be applied for the selection of joints for SPECT or SPECT/CT imaging. Prioritization for joint selection may be revised after review of the first group of images. Any changes in the prioritization for joint selection will be communicated to investigators prior to the fulfillment of additional doses. Images will be obtained with bilateral joints in the field of view, including both hands, shoulders, elbows, knees.

"Greatest interest" will be defined as the joint of highest Tc99m localization on imaging and as guided by concordance with DAS 28 finding.

1. Joint A will be a the joint of greatest interest as defined above from the planar imaging session. In the event a determination could not be made due to equivalent localization in multiple joints, the hands will be selected as joint A. 3D SPECT or SPECT/CT of Joint A will occur after the 60 and 180 minute whole body scan.
2. Joint B will be the joint of second greatest interest (knee or elbow or shoulder) or the hands if not already imaged as Joint A. 3D SPECT or SPECT/CT of Joint B will follow the 180 minute whole body scan.

3. Joint C would be imaged in the event that Joints A or B were no longer identified as a joint of interest from the 180 minutes whole body imaging. Joint C would be determined by the interest and the discretion of the investigator.

In the event all DAS 28 joints are negative for joint localization on whole body imaging, SPECT/CT may be performed on other areas of localization. A visual representation of the Visit 2, Day 1 imaging procedures for subjects enrolled in Groups 1-9 can be found in [Appendix 2](#).

It is anticipated that each SPECT or SPECT/CT scan would be acquired (at one bed position) for 25-30 minutes (30 minutes preferred). A break should address the comfort of the patient, encouraging the subject to void, consume fluids or food and to move or rest freely. For areas of low activity uptake, the SPECT scan may need to be increased. It is very important that the subject remain motionless for the duration of the 3D SPECT scan.

The SPECT transverse slices will be reconstructed using the manufacturer's recommended reconstruction algorithms including the recommended attenuation correction.

It is strongly recommended that each site should perform all imaging acquisitions per their camera manufacturer and model parameters and in accordance with their institutional practices for both the whole body scan, planar imaging, as well as the SPECT and SPECT/CT imaging acquisitions.

De-identified DICOM (Digital Imaging Communications in Medicine) copies of all acquired images will be transmitted to Navidea Biopharmaceuticals. The areas of localization will be identified, documented and captured in the eCRFs (electronic case report forms).

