3.3 Protocol Adherence

Strict adherence to all specifications outlined in this protocol is required for all aspects of the study conduct; the investigator may not modify or alter the procedures described in this protocol. If protocol modifications are necessary, all alterations that are not solely of an administrative nature require a formal protocol amendment for the involvement of Institutional Review Board(s) (IRB(s)).

If an investigator has deviated from the protocol in order to eliminate an immediate hazard to subjects or for other inevitable medical reasons, the investigator shall document all such deviations, including the reasons thereof, and submit the document to the sponsor and the IRB as applicable.

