9.3 Efficacy Variables

The efficacy variables for this study are as follows:

- Nuclear medicine specialist qualitative determination of presence/absence of radiotracer uptake (i.e., Tc 99m tilmanocept localization positive/negative) relative to background from SPECT imaging results for each DAS28 joint location for each subject (deemed the “gold standard” result, 28 joint locations per subject)
 - Clinically identified presence/absence of RA using the DAS28 instrument (28 joint locations per subject)
- Quantitative planar imaging intensity of radiotracer uptake for each joint location

A location/joint would be considered clinically identified as RA positive if it is either swollen or tender as measured by the DAS28 instrument. The presence of radiotracer uptake relative to background as determined by the nuclear medicine specialist at a location would indicate the location is RA positive.

The efficacy endpoints for this study are as follows:

- Per subject localization rate of Tc 99m tilmanocept by SPECT imaging
- Per joint location clinically RA-identified joint localization rate of Tc 99m tilmanocept by SPECT imaging

- Concordance of Tc 99m localization with anatomical areas of active RA defined by clinical symptomology.
- Localization intensity for each clinically RA-defined joint (as determined by quantitative SPECT gamma counts)
- Per subject localization rate of Tc 99m tilmanocept in areas other than RA-positive joints by SPECT imaging
- The following PK parameters will be calculated for each subject, whenever possible, using Tc 99m tilmanocept total radioactivity in whole blood and urine: maximum observed concentration (C_{max}), time to C_{max} (t_{max}), area under the concentration-time curve (AUC) from Hour 0 to the last measureable concentration (AUC_{0-t}), AUC extrapolated to infinity ($AUC_{0-\infty}$), apparent terminal elimination rate constant (λ_z), and apparent terminal elimination half-life ($t_{1/2}$).
- Radiation dosimetry of Tc 99m tilmanocept will include radiation doses per organ ($\mu\text{Gy}/\text{MBq}$), organs receiving the highest organ dose (HT), effective doses per organ ($\mu\text{Sv}/\text{MBq}$), mean effective dose ($\mu\text{Sv}/\text{MBq}$), effective dose resulting from a diagnostic dose $\pm 20\%$. Dosimetry will be based on target organ image counts and modeling per OLINDA/EXM® 2.0 software.

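### Joint intensity is defined as counts with no stated scaling, while scan times vary, the hand-image time is stated two ways, and sites are pointed to their own imaging practice

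*Combined protocol and SAP*

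**What the plan says.** **Acquisition.** Section 8.3 asks for a dual-headed camera with a low-energy, high-resolution collimator and a 15% window, with the allowance that "20% can be used if 15% setting not available". Section 3.3 adds that "the investigator may not modify or alter the procedures described in this protocol". Later, 8.3 strongly advises every site to use the settings of its own camera make and model, and to work "in accordance with their institutional practices for both the whole body scan, planar imaging, as well as the SPECT and SPECT/CT imaging acquisitions". It also makes SPECT reconstruction and attenuation correction follow the manufacturer.

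**Scan time.** Section 7.2.2.3 lists "Planar image with both hands in the FOV (5 min anterior/posterior views"; Section 8.3 says the hand image "should be acquired for ~ 5-7 minutes in both the anterior and posterior view". A SPECT scan is expected to take 25-30 minutes and may be lengthened for low uptake. The whole-body scan has a target of 5-7 million counts, which 8.3 expects may be reached sooner at higher activity.

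**Endpoint.** Section 9.3 lists "Localization intensity for each clinically RA-defined joint (as determined by quantitative SPECT gamma counts" as an endpoint, but its variable list names a planar intensity for each joint location. Section 9.5.3 summarises intensity by joint location and time point, without a split by dose group. Section 2.2 makes the comparison of intensity between dose groups a secondary objective, meant to inform the choice of dose and imaging time. Decay correction is stated for blood samples (8.4) and not for joint counts.

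**The concern.** A count depends on how long the camera looked, how much activity was given, how far it had decayed and how sensitive the camera was, as well as on uptake. The plan leaves the first three free to vary, points sites to their own practice on camera settings, and states no scaling for any of these. The dose-group and time-point comparisons named in Section 2.2 could then partly compare scan times, activities and cameras.

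The hand image matters most here. If the wrists are in view, it covers 22 of the 28 DAS28 joints in Appendix 5 (2 wrists, 10 MCP, 10 PIP). Scan length can also respond to activity or uptake, so it need not vary at random across dose groups.

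**Working it through.** The documents give no sample size, power, effect size or SD for intensity, so there is no planned figure to reproduce. The check asks how far counts can differ when true uptake is equal.

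**Model.** Expected counts = uptake fraction × administered activity × decay factor × camera sensitivity × acquisition time.

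**Inputs.** Hand time 5 min (7.2.2.3) and about 5-7 min (8.3); SPECT time 25-30 min (8.3); activity within ±20% of assignment (5.2); assigned activity 1, 5 or 10 mCi (5.2, Table 1); imaging at 60 ± 15 and 180 ± 15 min (7.2.2.3); Tc 99m half-life 6.02 h (abbreviation list).

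**Largest ratio of counts at equal uptake, one factor at a time**
- Hand time: 7/5 = 1.40.
- SPECT time: 30/25 = 1.20, and more if the scan is lengthened.
- Activity tolerance within one dose group: 1.2/0.8 = 1.50.
- Imaging window of ±15 min, a spread of 0.5 h: exp(ln 2 × 0.5/6.02) = 1.06.
- Hand time, tolerance and window together: 1.40 × 1.50 × 1.059 = 2.22.
- Assigned activity across groups: 10/1 = 10-fold; with tolerance, 12/0.8 = 15-fold.

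**Time points.** From 60 to 180 min, decay alone multiplies counts by exp(−ln 2 × 2/6.02) = 0.794, a fall of 20.6% that is not biological. It bears directly on the choice of imaging time.

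**Count target.** Suppose a whole-body scan is run to 6 million counts and a joint holds 0.2% of them (both assumed for illustration). The joint then shows 12,000 counts at 1, 5 and 10 mCi alike. Without the acquisition time, the activity difference cannot be seen.

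**After scaling.** Counts per minute bring the 1.40 to 1.00. Counts per minute, decay-corrected and per administered mCi, bring the 2.22 to 1.00. Camera sensitivity, energy window and reconstruction remain, and the documents do not quantify them.

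**Within-image ratio, for comparison.** Take assumed uptakes of 30 and 15 units in two joints of one image. With 5 min, 8 mCi and sensitivity 1.00, the first joint gives 30 × 5 × 8 = 1,200 counts. With 7 min, 12 mCi and sensitivity 1.15, it gives 30 × 7 × 12 × 1.15 = 2,898. The ratio to the second joint is 2.0 both times. If uptake is equal on both sides, the ratio is 1.0 at any level of uptake.

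**The case against.** **The contradictions are mild.** Five minutes lies inside about 5-7. The site-practice sentence is a recommendation and can be read alongside the settings in 8.3, which also require daily quality control and a thickness measure for attenuation correction of the whole-body views. The wider window is allowed only where the narrower is unavailable. This stands as far as it goes, but the text does not say which instruction prevails, and the missing scaling does not depend on it.

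**Hand time is planar, and the endpoint says SPECT.** True. Hand time reaches the endpoint only through the planar variable in 9.3; for SPECT, the stated variation is 25-30 minutes, extendable. The mismatch itself needs resolving.

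**The SAP may supply the scaling.** Section 9.5.3 defers other efficacy analyses to a SAP, and the document as supplied has no separate SAP text. So the gap can be asserted only for the protocol. But 9.5.3 itself sets the intensity summary, and later scaling cannot undo different windows or reconstructions.

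**Stronger readings that the documents do not support**
- *The bilateral view would cancel the problem.* Section 8.3 does say "Images will be obtained with bilateral joints in the field of view, including both hands, shoulders, elbows, knees", so a reader might infer that a left-right ratio is the answer. It removes shared multiplicative factors, but not differences in reconstruction, resolution or scatter. It also removes any dose effect common to both joints, which Section 2.2 wants to see. Nor are clinically negative joints a clean reference: DAS28 is assessed once, at screening (8.1.3), and Section 9.3 treats uptake in such joints as an endpoint of its own.
- *Pairing would bring a large gain in precision.* The documents give no CVs. For a comparison between dose groups, the variance gain from a log ratio is (b² + w²)/(2w²). With assumed between-subject CV b of 30-70% and within-subject CV w of 20-30%, it runs from (0.09 + 0.09)/0.18 = 1.0 to (0.49 + 0.04)/0.08 = 6.6. There may be no gain at all.
- *Site is confounded with dose.* If sites recruit equally and independently, a group of three comes wholly from one site with probability 3 × (1/3)³ = 1/9 for three sites and 2 × (1/2)³ = 1/4 for two. The synopsis allows about 1-3 centres; with one centre and one camera the issue disappears.

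**Conclusion.** The concern holds as a gap in standardisation and scaling. As written, joint counts have no stated common scale across subjects or time points. Equal uptake can give hand counts 1.40-fold apart from scan time alone, or up to 2.22-fold with the activity tolerance and imaging window at their extremes. Decay lowers counts by 20.6% between the two main imaging times. These are limits from the documents' own ranges, assuming counts proportional to time and activity; they do not predict typical differences. Any effect of site or camera comes on top and cannot be sized here.

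The change should be made, but the weight is moderate. Intensity is a secondary, descriptive endpoint and the primary variable is safety (9.2). It matters because Section 2.2 ties it to the choice of dose and imaging time.

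**What to change.** 1. **Sections 7.2.2.3 and 8.3.** Reconcile the two hand-image durations into one. State that the settings in 8.3 prevail over institutional practice, keep the 20% window only where 15% is unavailable and record its use, and require the same camera and settings at all of a subject's time points.
2. **Sections 9.3 and 9.5.3.** Say whether intensity is planar or SPECT. Summarise it by dose group and time point, as well as joint location, as counts per minute, decay-corrected to administration and divided by the administered mCi. Dividing by mCi removes the direct effect of activity by design, so keep the unscaled counts available.
3. **Listings.** Show site, camera, window and acquisition time for each image.
4. **Optional.** Report a within-image joint-to-reference ratio as a supportive summary beside the scaled counts, with its limits stated.

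The cost is protocol wording, a derived variable and some loss of freedom for sites. Amendment 6 is dated 19 June 2018 and recruitment was planned to end in July 2018, so acquisition changes cannot standardise images already taken. For those, the scaling and the listing are what can still be done, provided that the scan durations were recorded.
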